For major surgery, inhibitor and anti-factor rFIXFc antibody testing should be performed 2 to 4 weeks prior to the scheduled surgery, pre-operatively on the day of surgery, 1-2 weeks post-surgery (Visit 3), and at the last post-operative visit (Visit 4). Visit 4 (Last Post-Operative Visit) occurs when the subject returns to a regular rFIXFc regimen, as determined by the Investigator, and is required only if the subject did not return to a regular rFIXFc regimen at Visit 3. For minor surgery, the testing may be performed at the Investigator's discretion.

On the day of surgery, subjects will be given a preoperative dose of rFIXFc as a bolus, and, in the case of emergency surgery, as soon as possible prior to the procedure. Pre-dose FIX activity levels will be sampled, followed by FIX peak (recovery) samples, 30 (\pm 5) minutes post-dosing. A repeat sample may be taken approximately 6 to 9 hours after the loading preoperative dose is administered or at an interval based on the local standard of care for determination of subsequent rFIXFc dosing. During the subject's hospitalization, FIX activity will be measured daily at the local laboratory and a plasma aliquot will be prepared for each blood sample drawn so that subsequent analysis at the central laboratory can be performed.

Doses higher than 100 IU/kg may be used in the context of surgery to achieve the required FIX levels to prevent bleeding. However, the maximum number of daily or every-other-day doses will not exceed the predicted accumulated C_{max} of approximately 150% of normal (normal ranges are 50% to 150% FIX activity). All surgical dosing plans will be discussed with and approved by the Sponsor Medical Monitor before surgery. All doses administered in the hospital will be captured in the eCRF.

Bleeding events caused directly by surgery should not be recorded, although undesired or unexpected bleeding during or after surgery should be recorded on the eCRF.

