5.3.3. Surgical/Rehabilitation Period

The broadest span of time for the surgical/rehabilitation period in study 9HB01EXT is from the first dose of rFIXFc in study 9HB01EXT given for the surgery (i.e., the pre-surgery dose) up to 1) 1 minute before the first regular prophylactic dose after the last day of post-operative care/rehabilitation for subjects on prophylactic regimens and/or 2) 23:59 on the last day of the surgical/rehabilitation period for subjects on the episodic regimen. If dose(s) labelled for a surgical reasons which do not correspond to a surgery will be re-classified as 'OTHER' and will not be used in the determination of the surgical/rehabilitation period. Since not all subjects will have these events, specific considerations for the start and end of the surgical/rehabilitation period are as follows:

Start of the surgical/rehabilitation period:

- Date/time of the first pre-surgical dose. In general, if an injection for a pre-surgical dose is recorded in the eCRF, the reason for the injection should be labelled as "prophylaxis pre-operative". If an injection for pre-surgical dose is recorded in the EPD, the reason will be labelled as "surgical prophylaxis". If the date/time of surgery is complete, a pre-surgery dose is any dose labelled for a surgical reason on the day of, or the day before surgery, which is prior to the start date/time of the surgery. If the time of surgery is missing or 00:00 (as sometime occurs for minor surgeries), only

injections labelled as “prophylaxis pre-operative” on the day of surgery should be taken as a pre-surgical dose along with any other doses labelled for a surgical reason on the day before surgery. If there is more than one pre-surgical dose, then the first one should be selected (a pre-surgical dose can be administered the day before the surgery).

- If there is no pre-surgical dose but there was a prophylaxis dose or dose given for ‘OTHER’ reason prior to the surgery on the day of or the day before surgery, the last of these doses should be selected.
- If there is no pre-surgical dose, a prophylaxis dose, or dose for ‘OTHER’ reason prior to the surgery on the day of or the day before surgery then select the start date/time of the surgery. If the time was not recorded or recorded as 00:00 then select the date and impute 00:01 for the time.

End of the surgical/rehabilitation period:

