If the treatment regimen after the surgical/rehabilitation period is a prophylactic regimen, then the end of the surgical/rehabilitation period is:

- 1 minute before the first prophylactic dose on or after the last date among the dates for discharge from the hospital, post-operative visit 1, post-operative visit 2, the end of rehabilitation.
- If all of the dates mentioned above are missing, then select the first prophylactic dose after the date/time for the end of surgery. If the surgery time was not recorded or recorded as 00:00, then select the surgery date and impute 23:59 for the time. If the end date of the surgery is missing, then select the start date of the surgery and impute 23:59 for the time.
- If there are no prophylaxis doses following the latter of the 6 dates mentioned above, then select the latter of the dates and impute 23:59 for the time if otherwise there is no time associated with the given date (e.g., the subject completed the surgical/rehabilitation period but received no further prophylactic doses).
- If the overall end of study is declared while the subject is still in the surgical/rehabilitation period, then select the date of the end of study and impute 23:59 for the time.

If the treatment regimen after the surgical/rehabilitation period is the episodic regimen, then the end of the surgical/rehabilitation period is:

- Imputed as 23:59 on the last date among the dates for discharge from the hospital, post-operative visit 1, post-operative visit 2, and the end of rehabilitation
- If all of the dates mentioned above are missing, then select the date of the end of surgery and impute 23:59 for the time. If the end date of the surgery is missing, then select the start date of the surgery and impute 23:59 for the time.

Two exceptions are noted:

- If 2 (or more) major surgeries are performed without an intervening discharge from the hospital, then the first surgical/rehabilitation period will end 1 minute before the

start of the next surgery and the second surgical/rehabilitation period will end as described above.

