7.6. Surgery Data

Due to the small overall size of the Surgery Subgroup as described in Section 4.4, efficacy analyses will predominantly be based on assessment of subject data listings.

The following information will be provided in the data listings:

- Dates/times for the various components of the surgical rehabilitation period (hospital admission, surgery, and discharge)
- The surgical procedure performed, blood loss, and drainage
- Blood products used including details for type of transfusion, date/time administered, and amount given
- Surgeon's/Investigator's assessment of hemostatic response to rFIXFc
- Dosing during surgery, on the day of surgery, and for the first 14 days post-surgery (Days 1-3, Days 4-14, and Days 1-14)
 - during surgery: number of injections, average dose per injection, and total dose required to maintain hemostasis
 - day of surgery: total dose required to maintain hemostasis
 - post-surgery: total rFIXFc administered, the total number of injections, and the minimum and maximum intervals of time between injections
- The number of injections required to maintain hemostasis and average daily dose on the day of surgery and for Days 1-3 and Days 4-14 following surgery
- Injections and bleeding episodes during surgery and for the first 14 days following surgery, FIX levels, reason for injection, nominal dose, hours since the last injection, and if any additional treatment was given to treat the bleed

The following information will be summarized for the FAS:

- Number of injections and mean and total dose per injection required to maintain hemostasis during the major surgical period
- Estimated blood loss during major surgery
- Total rFIXFc consumption (IU/kg) per major surgery
- Number of bleeds after surgery per major surgery

In addition, minor surgeries will be summarized and listed where possible in a similar manner for the FAS.

During surgery includes the pre-surgery dose given for the surgery. The day of surgery refers to the calendar day of the surgery and includes the pre-surgery dose given for the surgery, even if it was given on the previous day. Day 1 refers to the day following surgery. The average dose per injection will be determined as the average dose across all injections during the referenced time period. Total dose will be determined as the sum of all doses administered during the referenced time period.

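### Under SAP 5.3.3 the periods of consecutive major surgeries can overlap, so surgical injections and doses can be counted under both surgeries

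*SAP*

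**What the plan says.** **Start of a period.** SAP 5.3.3 starts a surgical/rehabilitation period at the "Date/time of the first pre-surgical dose". When the date and time of surgery are complete, "a pre-surgery dose is any dose labelled for a surgical reason on the day of, or the day before surgery", provided that it precedes the operation. "If there is more than one pre-surgical dose, then the first one should be selected". If no surgically labelled dose qualifies, the last prophylaxis or OTHER dose on those two days is used. Only if there is none of these does the period start with the operation itself.

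**End of a period.** For a subject who goes on to prophylaxis, the period runs to just before the first regular prophylactic dose once the latest of that surgery's own dates is reached (discharge, post-operative visits, end of rehabilitation). For a subject on the episodic regimen it runs to the end of that latest date.

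**Exceptions.** There are two. One applies when a subject has two or more major operations and does not leave hospital in between; it closes the earlier period a minute ahead of the "start of the next surgery and the second surgical/rehabilitation period will end as described above". The other exception covers a minor surgery inside the period of a major one.

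**Use.** SAP 7.6 summarizes the number of injections and the dose over the major surgical period, "Total rFIXFc consumption (IU/kg) per major surgery", and the number of bleeds after each major surgery. It defines total dose as a sum over every dose in the time period concerned. Protocol 10.1.3 makes a pre-operative dose routine: "On the day of surgery, subjects will be given a preoperative dose of rFIXFc as a bolus".

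**The concern.** The no-discharge exception seems meant to make two periods meet. It closes the first by reference to the second operation, whereas the second period opens at an earlier event, the pre-surgical dose. SAP 5.3.3 itself treats these as different events, because the operation's start is only the fallback when no dose qualifies. Where there was a discharge, no rule closes the first period at a later major surgery at all.

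Injections and dose to maintain hemostasis are a named major surgery endpoint (SAP 2.2.3). SAP 7.6 calls the Surgery Subgroup small, so a single pair of surgeries of this kind could move a mean or a maximum. Without a rule, the programmer decides which surgery a dose belongs to.

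**Working it through.** The plan gives no figure to reproduce. The check applies the SAP 5.3.3 rules as written to assumed timelines, since the documents contain no surgery dates. A is the earlier surgery and B the later.

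**1. No discharge: the two anchors.**
- End of period A = start of operation B − 1 minute.
- Start of period B = first qualifying dose on the day of operation B or the day before.
- Overlap = (start of operation B − 1 minute) − (first qualifying dose for B).
- Simplest case: dose at 08:00, operation at 09:00. A ends at 08:59 and B starts at 08:00. The 08:00 dose is in both.
- Longest case: dose at 00:00 the day before, operation at 23:59. Overlap = 47 h 58 min.
- With no qualifying dose, B starts with the operation and there is no overlap.

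**2. No discharge: dose count.** Operations on 3 and 10 March at 09:00. Surgical doses at 08:00 on 3, 4, 5, 7, 9, 10, 11, 12, 14 and 17 March (10 doses). Regular prophylaxis resumes on 26 March at 08:00.
- Period A: 3 March 08:00 to 10 March 08:59, 6 doses.
- Period B: 9 March 08:00 to 26 March 07:59, 6 doses.
- Overlap 24 h 59 min. Counted 6 + 6 = 12 against 10 given, so 2 are counted twice.

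The 9 March dose may have been given for recovery from A. It still opens period B, because any surgically labelled dose on the previous day qualifies. The number of shared doses is therefore one or more.

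**3. Discharge between the surgeries: dose count.** Operations on 3 and 20 March at 09:00. Surgical doses at 08:00 on 3, 4, 5, 7, 10, 13 and 16 March (7), then on 20, 21, 22, 24, 27 and 30 March (6), 13 in all. The latest date for B is 3 April.

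| Case | A ends | Counted | Twice |
|---|---|---|---|
| Prophylaxis, A's latest date 17 March, next regular dose 8 April 08:00 | 8 April 07:59 | 13 + 6 = 19 | 6 |
| Same, but a regular dose on 18 March 08:00 | 18 March 07:59 | 7 + 6 = 13 | 0 |
| Episodic, A's latest date 17 March | 17 March 23:59 | 7 + 6 = 13 | 0 |
| Episodic, A's latest date also 3 April | 3 April 23:59 | 13 + 6 = 19 | 6 |

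In the first and last rows period A contains all of period B. This needs a condition. On prophylaxis, no regular dose falls between the surgeries on or after A's latest date. On the episodic regimen, A's dates run into or past B's period.

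**4. Which outputs are exposed.** The summary of injections and dose refers to the surgical period, so it is exposed directly. SAP 7.6 gives no window for consumption or bleeds per major surgery, so they are exposed only if they use the same period. Without a discharge the overlap ends before operation B, so B's post-operative doses and bleeds cannot fall in A. They can do so only in the discharge case.

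**5. Illustrative size.** The documents give no total dose per surgery. Assume one shared dose of 100 to 150 IU/kg (150 is the single-dose maximum in protocol 15.4.1) and a true total of 500 to 800 IU/kg, a range with no source in the documents. That surgery's total then rises by between 100/800 = 12.5% and 150/500 = 30% per shared dose.

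**The case against.** The strongest reply is that adjoining periods were plainly intended. SAP 5.3.1 uses the same 1-minute device to make successive regimens meet, and a sensible programmer might take the start of the next surgery to mean the start of its period. That is plausible, but it is not what SAP 5.3.3 says, and it does nothing for surgeries separated by a discharge.

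A second reply is that double counting is inferred. This stands in part. The SAP nowhere says that a dose is counted twice. Many dose items in SAP 7.6 have windows of their own (during surgery, day of surgery, Days 1-3, 4-14 and 1-14). The SAP's list of tables titles the injections table as during major surgery; if that means the intra-operative window only, its counts are not doubled. However, SAP 2.2.3 and 7.6 both describe the endpoint over the surgical period, so the title is more naturally shorthand. SAP 5.3.3 does refer to the last dose given for the surgery, but only to delimit post-operative care. SAP 7.6 does not use it to allocate doses.

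Third, surgery results are to be assessed mainly from listings, where an overlap could be seen. That limits the harm but does not supply a rule.

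A reader might go further and infer that the later surgery's doses and bleeds are always charged to the earlier one, or that bleeding rates are distorted. The documents support neither. Step 4 rules out the first without a discharge, and step 3 shows that with a discharge it is conditional. SAP 5.3.2, 6.5.4 and 7.1 take all surgical time out of the efficacy period, so overlap there does not count anything twice.

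**Conclusion.** The point holds as a defect in a stated rule, and it is minor. Without a discharge, overlap is the expected result whenever the exception applies, because a pre-operative dose is routine. After a discharge, containment is possible but not automatic. Injections and dose during the major surgical period can then be counted under two surgeries.

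The size is unknown. The documents do not show that any such pair of surgeries occurred, and the percentages in step 5 rest on assumed totals, so they should not be read as an estimate of bias. The primary endpoint, annualized bleeding rate and annualized consumption are not double counted.

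**What to change.** Replace the no-discharge exception in SAP 5.3.3 with wording such as:

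> If the surgical/rehabilitation period of a further major surgery begins before that of an earlier one has ended, with or without an intervening discharge, the earlier period ends 1 minute before the next period starts. Where there was an intervening discharge, the last period ends at the latest of the end times otherwise defined for any of these surgeries. Each dose is assigned to one major surgery only; a dose recorded as post-operative for the earlier surgery does not start the later period.

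SAP 7.6 should also name the window used for consumption and bleeds per major surgery.

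**Check on step 2.** If the 9 March dose is recorded as post-operative for A, the counts become 5 + 5 = 10; otherwise 4 + 6 = 10. No dose is counted twice.

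**Why the latest-end sentence is needed.** Suppose A's rehabilitation ends on 20 April, B's latest date is 1 April, and a regular prophylactic dose is given on 5 April. If A were simply cut at the start of B, the surgical time would end just before the 5 April dose. The time from then until the first regular dose on or after 20 April would enter the efficacy period and alter the annualized rates. With the sentence, the time excluded from the efficacy period stays as it is now.

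The electronic diary label for surgical doses does not separate pre-operative from post-operative, so the program specification should say which surgery takes a dose carrying only that label. The cost is a few lines of SAP text and programming, with no new data.

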5.3.4. Safety Period

The safety period is defined as the period from 9HB01EXT Study Day 1 to the last recorded date. The end of the safety period will be imputed as 23:59 for the time on the last recorded date in the analysis database. The last recorded date is either the date of the last study visit, last telephone call, or the date of the last dose, whichever comes last.

5.4 Electronic Patient Diary (EPD) Data/eCRF injections

Subject recorded diary data was originally queried via a defined process which required confirmation with the subject of **all** changes. Taking into consideration audit findings and industry standards to limit changes of subject reported data, the query process was updated to **only allow changes defined as not requiring subject confirmation**. Although consolidation of records of single vials recorded within 60 mins of each other (SVC/L60) was classified as a change not requiring subject confirmation (as agreed with MHRA in 2014), these changes are no longer being made directly into the data, but will be applied via a programmatic data convention. In addition, true duplicate records resulting from administrative issues and hence not requiring subject confirmation of the change will be deleted. These programming algorithms to address these two scenarios are described as follows:

1) Record consolidation:

When a dose requires more than one vial and these vials are erroneously recorded in the EPD/eCRF as separate injections, albeit within a short time window, the change to consolidate these multiple records into one record is called Single Vial Consolidation (SVC). Based on the EPD set up, the programming algorithm to identify and consolidate the records is as follows:

- Identify all injection records within 60 minutes of one another where the variables (injection date/times, lot numbers, number of vials, and vials strength in nominal IU) are not exactly the same on each record. There are three scenarios:
 - a) Date and time of injections **are not** exactly same, and lot numbers, number of vials, and vials strength in nominal IU **are not** the same.
 - b) Date and time of injections **are** exactly same, but lot numbers, number of vials, and vials strength in nominal IU **are not** the same.
 - c) Date and time of injections **are not** exactly same, but lot numbers, number of vials, and vials strength in nominal IU **are** the same.
- Consolidate injections as follows:
 - Record with earliest injection date/time retained with corresponding contextual information
 - Combine/sum values related to the dose (e.g. lot numbers, number of vials, volume injected, nominal and actual dose) into the single retained record

One exception to note: if injections identified with the above algorithm have distinctly different reasons (e.g. one injection is recorded as bleed or surgery and another is recorded as prophylaxis, additional, or OTHER), then the records should NOT be consolidated.

2) True duplicates removal:

When injections are identified in the EPD with exactly the same date/times, lot numbers, number of vials, and vials strength in nominal IU, due to the EPD set up, these must have resulted due to administrative issues and are therefore true duplicates. There are four types of administrative issues as follows:

- a) Technical transmission issue;
- b) Entry of same record into 2 different devices;
- c) Duplicate manual entries; and
- d) Records duplicated in EPD and eCRF, which although could be removed via the query process, still remain

The programming algorithm to identify and delete the duplicates is as follows:

- Identify all injections that have exactly the same date/times, reasons for injection, lot numbers, number of vials, and vials strength in nominal IU
- Remove the duplicates and keep a single record. However, if injections have distinct reasons, such as one injection that is recorded as prophylaxis and another has no reason recorded (blank), the injection with prophylaxis is kept.

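### A dose entered twice a few minutes apart is summed as if it were two vials, because SAP 5.4 removes duplicates only when the recorded times match exactly

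*SAP*

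**What the plan says.** SAP 5.4 defines two programmed corrections to the injection data.

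*Consolidation.* The stated purpose is to rejoin vials of one dose that were logged as separate injections. The instruction is to "Identify all injection records within 60 minutes of one another" where the record fields are not all identical. Three scenarios follow. Scenario (c) reads "Date and time of injections are not exactly same, but lot numbers, number of vials, and vials strength in nominal IU are the same". The action is to keep the earliest record and "Combine/sum values related to the dose (e.g. lot numbers, number of vials, volume injected, nominal and actual dose) into the single retained record". The one exception is records with distinctly different reasons for injection; "then the records should NOT be consolidated".

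*Duplicate removal.* The listed causes include "Duplicate manual entries" and "Records duplicated in EPD and eCRF, which although could be removed via the query process, still remain". The removal step is to "Identify all injections that have exactly the same date/times, reasons for injection, lot numbers, number of vials, and vials strength in nominal IU" and keep one.

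SAP 5.4 and 9 also describe the query process. After the audits it permits only changes that need no subject confirmation. In the Section 9 code table, deleting a diary entry that also exists in the eCRF as an in-clinic dose (D/CRF) needs no confirmation. Deleting a double entry within the diary (D/EPD) does need it. The impact assessment returns every change that required confirmation to its pre-change value.

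**The concern.** The two steps leave a gap. A dose entered twice at slightly different times fails the duplicate test, because the times differ, and meets scenario (c), because everything else agrees. The duplicate is then added to the dose. No step compares the summed dose with the prescribed dose, checks whether the two records come from different sources, or looks at vial accountability.

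The results at stake are those built on IU per record: annualized consumption (SAP 6.5.4, a secondary endpoint), average weekly prophylactic dose (6.5.3), dose per injection and total dose to resolve a bleed (7.4.1), and prophylactic dose compliance (6.5.5.2).

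**Working it through.** The plan gives no figure for this rule, so there is none to reproduce. The check applies the two steps of 5.4 to test records and then sizes the effect.

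**1. The rule applied.** The test dose is one 3000 IU vial, a strength listed in Protocol 12.1. Exact-match removal comes first, then 60-minute consolidation of same-reason records.

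| Test case | Records kept | Total IU | True IU |
|---|---|---|---|
| One dose, entered twice at the same minute | 1 | 3000 | 3000 |
| One dose, entered twice 5 minutes apart, same reason | 1 | 6000 | 3000 |
| Two vials of one lot, logged 5 minutes apart, same reason | 1 | 6000 | 6000 |
| One dose, entered twice 5 minutes apart, different reasons | 2 | 6000 | 3000 |
| One dose, entered twice 90 minutes apart, same reason | 2 | 6000 | 3000 |

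Rows 2 and 3 have identical inputs, so the rule cannot tell a double entry from a genuine split. In rows 4 and 5 nothing is summed, but total IU is still double-counted. For consumption, then, the underlying fault is that near-time duplicates go undetected. The summing adds a distorted dose per record.

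**2. Which double entries can survive.**
- Diary plus eCRF, in clinic: D/CRF is coded as needing no confirmation, so a query can remove it.
- Twice in the diary: D/EPD is coded as needing confirmation, so the current process cannot delete it. The impact assessment restores those previously deleted. If a restored pair lies within 60 minutes at different times, scenario (c) sums it.

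**3. Ceiling for the in-clinic route.** Visits are 6-monthly (Protocol 7.1), with trough and peak samples around an infusion for prophylaxis subjects (Protocol Table 1, footnote 10). Assume one in-clinic dose per visit, hence 2 a year, and that every one is doubled:
- weekly dosing: 2/52 = 3.8%
- 14-day dosing: 2/26 = 7.7%

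These denominators count prophylactic doses only; including bleed treatment would lower both percentages.

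**4. Diary route.** Frequency is unknown and not bounded by visits. If a share *s* of doses is double-entered, consumption is multiplied by (1 + *s*). At an assumed 50 IU/kg weekly, the true value is 50 × 365.25/7 = 2608.9 IU/kg/year. It becomes 2635.0 at *s* = 1%, 2661.1 at 2%, 2739.4 at 5% and 2869.8 at 10%. These shares are assumptions.

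**5. Compliance.** A dose taken as prescribed and then doubled scores 200%, outside 80% to 125%. At the step 3 ceiling, a subject otherwise fully compliant would score 50/52 = 96.2% or 24/26 = 92.3%, still above the 80% cut-off for being counted dose compliant.

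**6. What does not move.** One record is retained, so the summing adds no injection, exposure day or bleed. Inhibitor results do not use these records.

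**The case against.** Scenario (c) is needed. Several vials of one lot and strength, logged one at a time, give exactly this pattern, and summing them is right. The SAP bases the algorithm on the diary set-up, which the documents do not describe, so the frequency of near-time duplicates cannot be judged. In-clinic pairs have a query route, and Protocol 7.1.4.1 makes sites and monitors responsible for agreement between diary and eCRF. All analyses are descriptive, and injections are listed, so a record at twice the prescribed dose could be seen. All of this stands, and it limits the point to a minor one. It does not close the gap for double diary entries. The SAP's output list also names no listing that would show which records are sums.

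A reader might go further in four ways that the documents do not support.
- That the plan admits near-time diary/eCRF duplicates survive. The remark that some remain sits under duplicates with exactly matching times and says nothing about near-time pairs.
- That doubled doses would be reported as overdoses. A 100 IU/kg dose would appear as 200 IU/kg, above the 150 IU/kg definition. However, sites report overdoses on a separate form (Protocol 15.4.1), and SAP 8.2 keeps them out of the adverse event tables unless they are reported as such.
- That any two records within the hour are summed. Those with distinctly different reasons are not.
- That the regulator did not accept this algorithm. SAP 5.4 says only that the change category was agreed in 2014 as needing no confirmation; the agreement itself is not available.

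**Conclusion.** The point holds as a minor defect in a stated rule. As written, scenario (c) doubles a single dose entered twice within 60 minutes at different times and for the same reason, unless a query removes it. The diary-only case is the more exposed, because its query route is closed and the impact assessment brings such entries back. Section 9 does not list consumption among the endpoints that assessment reruns.

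The 3.8% and 7.7% figures are ceilings for the in-clinic route, not estimates. They assume that every clinic dose is entered twice, that each pair meets scenario (c), and that no query catches any. The documents give no frequency for either route. Bleeding rate, exposure and the primary endpoint are not inflated by the summing.

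**What to change.** In SAP 5.4:

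1. When one record is from the diary and the other from the eCRF, within 60 minutes and with identical lots, vial count and strength, keep one record instead of summing.
2. For same-source scenario (c) pairs, keep the summing rule, but list every such consolidation before lock, in both the main and the impact-assessment datasets.
3. On that listing, flag prophylactic records whose summed dose exceeds 125% of the prescribed dose. This should prompt review and not decide consolidation. As a decision rule it would feed back into the compliance measure and could leave a genuine high multi-vial dose split. The SAP also defines no prescribed-dose comparator for bleed or surgical doses, so for those the listing is the only check.
4. As a sensitivity analysis, rerun consumption and the other dose-based summaries keeping one record of each flagged pair.

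The cost is a small programming change, one listing and one rerun, with no new data and no new subject confirmation. The downside is that a dose genuinely split between diary and eCRF, which should be rare, would be under-counted.
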